(4) Prior to beginning PET, informed consent will be obtained from eligible participants to reduce the possible risks of mild to moderate anxiety when exposed to anxiety-provoking images and situations in treatment sessions, at home or completing homework exercises. Each participant will be given a rationale for PET and advised of the treatment procedure and the temporary effects that the procedure might have. Participants will be required to give consent prior to every exposure exercise or task. PET has well-documented efficacy for reducing PTSD symptom severity (Foa et al., 1999, 2005, 2008; Powers et al., 2010). While a small proportion of individuals fail to benefit from PET, very few report adverse effects. The exposure exercises will be individually and gradually titrated such that in-vivo exposure exercises start with real-life trauma reminders that elicit moderate anxiety and progress to more anxiety-provoking stimuli.

(5) Participants in each condition will be informed by study staff that they may call between sessions should they experience a crisis or are distressed enough to need psychological support. If a therapist becomes concerned about a participant's psychological welfare, contact will be made with the PI who will arrange for psychological evaluation. Although unlikely, if substantial emotional reactions develop that require additional interventions, participants will be withdrawn from the study and referred to public health treatment providers to receive these services. Such identification can be made by research therapists in consultation with the PI.

(6) In cases where danger to self or others is identified, the participant will be withdrawn from the study and clinically appropriate emergency service procedures will be implemented. In cases where a participant is determined to be a danger to self or others, the PI or qualified study staff member will assess the individual's level of risk and work with the participant to develop a safety plan. Study staff will also provide the participant with relevant educational material, contact information for national and local crisis services, and referrals to local counseling services. In cases where a participant is determined to be at imminent risk for harm to self or others, the PI will make referrals for more intensive psychiatric services and arrange for transportation to these facilities when necessary.

(7) Risks associated with OAT as usual may include non-reduction of PTSD symptoms.

Potential Benefits to Participants and Others

Participants may benefit by experiencing reductions in PTSD symptoms during their study participation, including reductions in substance use problems as well as the wide range of medical, psychiatric and psychosocial consequences associated with PTSD. They may also benefit from the financial compensation provided as part of the proposed study. The present study stands to provide scientific benefits by expanding our empirical knowledge related to the mechanisms through which OAT and PET promote reductions in PTSD symptomatology in a highly vulnerable clinical population. Furthermore, by providing PET to individuals with concurrent PTSD and OUD, the proposed research also stands to benefit public health in general by reducing the personal and societal costs associated with PTSD (e.g., medical, psychiatric, and substance use treatment utilization and costs, suicidality, poor physical health and decreased quality of life) in patients with OUD. Overall, the individual participant, the medical and scientific communities, and society in general may benefit by our efforts to determine whether OAT alone may attenuate PTSD symptomatology even in the absence of intensive cognitive-behavioral therapy. As such, the risks to which individuals may be exposed as a function of their research participation are reasonable in relation to the anticipated benefits.

Importance of the Knowledge to be Gained

The proposed project has the potential to produce important new scientific and clinically-relevant information related to the mechanisms through which OAT and PET promote reductions in PTSD symptomatology in a highly vulnerable clinical population. Thus, knowledge gained from this research may significantly improve quality of life, psychiatric distress and psychosocial functioning in this vulnerable population, as well as public health more generally. Consequently, the risk/benefit ratio is favorable. The risks to which individuals are exposed as a consequence of their research participation are generally no more than that associated with continuing opioid treatment as usual. In contrast, the potential and probable benefits to be derived by society in general and by individuals with concurrent PTSD and OUD as a group are considerable. In summary, conducting this research seems well justified.

Therapeutic Alternatives: List the therapeutic alternatives that are reasonably available that may be of benefit to the potential subject and include in the consent form as well.

Not Applicable

Patients are free not to participate in this study or to withdraw from it at any time. Participants who decide not participate in the study will be offered clinically appropriate treatment referrals outside the study.

Data Safety and Monitoring: The specific design of a Data and Safety Monitoring Plan (DSMP) for a protocol may vary extensively depending on the potential risks, size, and complexity of the research study. For a minimal risk study, a DSMP could be as simple as a description of the Principal Investigator's plan for monitoring the data and performance of safety reviews or it could be as complex as the initiation of an external, independent Data Safety and Monitoring Board (DSMB). The UVM/UVM Medical Center process for review of adverse events should be included in the DSMP.

Patient eligibility and status. All intake data collection will be conducted by a trained bachelor's-level RA or doctoral- or master's-level research therapist using specialized forms and procedures. Intake information will be reviewed by the PI, who will determine participant eligibility. Only trained and IRB-approved research staff will complete informed consent with eligible and willing participants. The status of all active participants will be reviewed at weekly meetings between the PI and research staff.

Rigorous data management/Quality assurance. The majority of study data collection will be conducted using self-report questionnaires. All assessments will be administered by trained research staff. Randomly selected data will be checked by the RAs for completeness and to ensure quality (i.e., no appearance of rote answers, etc.). All subject data will be maintained in secure filing cabinets behind locked doors in order to protect confidential subject information. Safe places will include locked filing cabinets or locked rooms that will be accessible only to study personnel. Participant identity will be disguised using ID numbers keyed to a master list. Moreover, all data that are entered into spreadsheets and databases, in preparation for data analyses, will be entered twice. That is, two separate individuals will enter the data into databases, and a comparison between data entries will be conducted to detect data entry errors. All discrepancies in data entry will be checked against the raw data source, and the correct data entry will be used. All data that are entered into spreadsheets and databases will be password protected and coded by subject ID number and not by subject name. Additionally, all entered data will be backed up on a secure project server at least weekly. The biostatistician and PI will consult regularly to discuss ongoing data management and any problems that arise.

Auditing procedures. Review of any problems related to quality of data collection, transmission or analyses and of any AEs and SAEs that occurred during the past week will occur at weekly research staff meetings.

Define criteria to be used for decision making regarding continuation, modification, or termination of the entire study (not individual participation) (i.e. "stopping rules").

We do not anticipate early trial termination and thus do not have any a priori early stopping criteria.

What will be the frequency of the review? Please note that the frequency of reviews should be commensurate with the risk of the study. At a minimum, a review of the data should be conducted annually at time of continuing review. **Forward copies of the data and safety monitoring reports to the 1) IRB, 2) CRC (if applicable), and/or 3) UVMCC (if applicable).**

Monthly
 Quarterly
 Bi-annually

Annually
 Other (e.g. by dosing level, no. of subjects enrolled):

Will the sponsor be conducting data monitoring visits for this study?

Yes No NA

If yes, how often?

Adverse Event, Unanticipated Problem (UAP), Reportable New Information (RNI): Describe how events and UAPs will be evaluated and reported to the IRB. All protocols should specify that, in the absence of more stringent reporting requirements, the guidelines established in the "Adverse Event and Unanticipated Problems Reporting Policy" will be followed. The UVM/UVM Medical Center process for review of adverse events and UAPs to subjects or others should be included in the DSMP.

AEs and SAEs will be assessed at each clinic visit by a trained RA or research therapist. Any SAE will be brought to the attention of the PI as soon as possible and not longer than 24 hrs. Any SAE, whether or not related to study intervention, will be reported to the IRB's CHRBSS using the UVM Adverse Event Reporting Document within 5 days of the event. The CHRBSS will determine whether additional reporting requirements are needed. Any SAEs will also be summarized in the yearly IRB continuing review, including a review of frequency and severity.

Withdrawal Procedures: Define the precise criteria for withdrawing subjects from the study. Include a description of study requirements for when a subject withdraws him or herself from the study (if applicable).

OAT+PET and OAT+PET⁺ participants who miss four consecutive weeks of treatment no longer be eligible to continue in PET but will be eligible to complete follow-up assessments. Furthermore, continued enrollment in standard buprenorphine or methadone maintenance treatment is necessary for patients to continue in PET. Patients who drop out of buprenorphine or methadone maintenance treatment will no longer be eligible for the study and their participation will be terminated. Patients are free not to participate in this study or to withdraw from it at any time. If they decide not to participate in the study, we will be glad to discuss with them other clinically appropriate treatment referrals for PTSD that may be available in Vermont. If patients decide not to participate in this study or to withdraw from this study, their decision will not prejudice their future medical care.

Sources of Materials: Identify sources of research material obtained from individually identifiable human subjects in the form of specimens, records or data. Indicate whether the material or data will be obtained specifically for research purposes or whether use will be made of existing specimens, records or data.

Research materials will include questionnaires, structured clinical interviews, and urine samples for analyzing recent drug use. All data will be collected for research purposes only. All data collection will be conducted by a trained bachelor's-level RA or doctoral- or masters-level research therapist with special training on all forms and procedures. All information will be reviewed by the PI, who will determine participant eligibility and complete informed consent with eligible and willing participants. Subject data will be maintained in secure filing cabinets behind locked doors in order to protect confidential subject information. Safe places will include locked filing cabinets or locked rooms that will be accessible only to study personnel. Participant identity will be disguised using ID numbers keyed to a master list and data will be entered directly onto computer files that will be password protected. Computer files will carry only participant numbers for case identification. Session recordings of therapy sessions will be transferred to the secure UVM College of Medicine server. Subject data and subject identifiers will only be accessible to approved research staff who will be trained in the importance of confidentiality.

DRUG INFORMATION

Investigators are encouraged to consult the UVM Medical Center Investigational Pharmacy Drug Service ([name]) prior to finalizing study drug/substance procedures.

Drug (s)

Not applicable

Drug name – generic followed by brand name and common abbreviations. Availability – Source and pharmacology; vial or product sizes and supplier. If a placebo will be used, identify its contents and source.

Preparation: Reconstitution instructions; preparation of a sterile product, compounded dosage form; mixing guidelines, including fluid and volume required. Identify who will prepare.

Storage and stability – for both intact and mixed products.

Administration – Describe acceptable routes and methods of administration and any associated risks of administration.

Toxicity – Accurate but concise listings of major toxicities. Rare toxicities, which may be severe, should be included by indicated incidence. Also adverse interactions with other drugs used in the protocol regimen as well as specific foods should be noted. Address significant drug or drug/food interactions in the consent form as well. List all with above details.

Is it FDA approved: (include FDA IND Number)

1. in the dosage form specified? If no, provide justification for proposed use and source of the study drug in that form.

2. for the route of administration specified? If no, provide justification for route and describe the method to accomplish.

3. for the intended action?

**SUBJECT CHARACTERISTICS,
IDENTIFICATION AND
RECRUITMENT**

Subject Selection: Provide rationale for subject selection in terms of the scientific objectives and proposed study design.

Participants will be adults who are maintained on buprenorphine or methadone and have a current diagnosis of PTSD.

Vulnerable Populations: Explain the rationale for involvement of subjects (e.g., cognitively impaired, Non-English speaking, prisoners, students). Discuss what procedures or practices will be used in the protocol to minimize their susceptibility to undue influences and unnecessary risk (physical, psychological, etc.).

Not applicable

Inclusion/Exclusion Criteria: Eligibility and ineligibility criteria should be specific. Describe how eligibility will be determined and by whom. Changes to the eligibility criteria at a later phase of the research have the potential to invalidate the research.

Participants must be >18 years old and be currently maintained on a stable methadone or buprenorphine dose for \geq 1 month prior to the study. They must also endorse >1 traumatic event, meet current DSM-V PTSD criteria (American Psychiatric Association, 2013), and be willing to have therapy sessions audio recorded for the purpose of completing weekly homework assignments and have clear memory for the traumatic event. Individuals with an acute psychotic disorder, bipolar disorder with an active manic episode (but not simply the presence of bipolar disorder), imminent risk for suicide, a medical condition that may interfere with consent or participation (e.g., organic brain syndrome, dementia, head injury, neuropathy, etc.) will be excluded, as well those who demonstrate illiteracy in English.

Inclusion of Minorities and Women: Describe efforts to include minorities and women. If either minorities or women are excluded, include a justification for the exclusion.

The study will include minorities and women. We will do all that we can to assure that women and minorities are represented in the research, including using a wide range of recruitment sources to ensure that information regarding this project reaches as diverse of a population as possible (e.g., flyers posted in multiple local neighborhoods, advertisements in the widely-distributed primary local newspaper as well as alternative local papers).

Inclusion of Children: Describe efforts to include children. Inclusion is required unless a clear and compelling rationale shows that inclusion is inappropriate with respect to the health of the subjects or that inclusion is inappropriate for the purpose of the study. If children are included, the description of the plan should include a rationale for selecting or excluding a specific age range of children. When included, the plan must also describe the expertise of the investigative team in working with children, the appropriateness of the available facilities to accommodate children, and the inclusion of a sufficient number of children to contribute to a meaningful analysis relative to the purpose of the study. Provide target accrual for this population. Identify whether children are wards of the state. **If children are excluded** then provide appropriate justification.

Children will not be eligible for this study.

For protocols including the use of an investigational drug, indicate whether women of childbearing potential have been included and, if not, include appropriate justification.

N/A

If HIV testing is included specifically for research purposes explain how the test results will be protected against unauthorized disclosure. Include if the subjects are to be informed of the test results. If yes, include the process and provision for counseling. If no, a rationale for not informing the subjects should be included.

Not applicable

Will the SONA psychology Pool be utilized? *Include documentation indicating permission to use this recruiting tool*

Yes No

FINANCIAL CONSIDERATIONS

Describe all potential research related expenses to subjects:

There are no expenses to the subject for any aspect of the study.

Compensation for participation: Describe all plans to pay subjects, either in cash, a gift or gift certificate. Please note that all payments must be prorated throughout the life of the study. The IRB will not approve a study where there is only a lump sum payment at the end of the study because this can be considered coercive. The amount of payment must be justified. Clarify if subjects will be reimbursed for travel or other expenses.

Not applicable

All participants will receive \$60 for completing the initial intake assessment and \$150 for completing follow-up assessments at 4-, 8-, and 12-weeks post-randomization. In addition, OAT+PET⁺ participants will earn vouchers that have monetary value for attending scheduled PET appointments. Vouchers will be given to participants immediately following completion of each session. No cash will be provided to patients; rather, subjects will be able to submit vouchers to a research assistant in exchange for gift cards that they can use for purchase of retail items and services in the local community. The initial session will be worth \$20. Each consecutive attended session will increase the voucher amount by \$5 such that the 2nd consecutive session will be worth \$25, the 3rd \$30 and so on (Table 1).

To support completion of the full 12-week PET protocol, we will incorporate additional strategically-placed bonuses into the reinforcement schedule with the goal of maximizing the percentage of subjects who complete the full 12-session protocol. Bonuses have been a mainstay of our voucher-based interventions with other challenging populations (Alessi et al., 2004; Dunn et al., 2008, 2010; Higgins et al., 1991; Roll et al., 1996, Roll & Higgins, 2000; Sigmon et al., 2016). First, to support consistent (vs. sporadic) attendance, participants will receive a \$50 bonus for every two consecutive sessions attended (Table 1). Second, to support completion of the full PET protocol, participants will receive a \$100 bonus upon completion of Session 12.

Missed sessions will earn no vouchers and will reset the voucher values for the next attended session back to the initial \$20 value. Two consecutive attended PET sessions following a reset will return the voucher value back to the value immediately prior to the missed appointment. In prior studies, we demonstrated that this reset mechanism helps to maintain the momentum of behavioral change (Roll et al., 1996; Roll & Higgins, 2000). Overall, participants who are randomized to the OAT+PET⁺ group and who attend every PE session as scheduled can earn a maximum of \$920 for session participation combined across both regular and bonus incentive schedules.

Collaborating Institutions

Will this research be conducted in collaboration with other sites at other locations?

Yes No

If so, complete the following for all collaborating institutions:

Institution Name	Describe Involvement	Is there an IRB? If yes, attach approval or explanation	Are other permissions required? If yes, attach approval or explanation

INFORMED CONSENT

a. Type of Consent

i. Are you obtaining Written Consent?

If yes, will there be more than one consent document?

If yes, how many consent documents and for what populations.

	Yes		No
	Yes		No

Consistent with our prior IRB-approved studies, we will utilize both a Screening and Study consent. This procedure is effective in limiting the number of individuals who are enrolled into the actual randomized trial who are determined not to be eligible during the initial intake assessment visit.

ii. Are you requesting a Waiver of Informed Consent? Yes No

This request means that you will not be obtaining verbal nor written consent. **If yes**, complete the form Request for a Waiver of Informed Consent/Authorization/Documentation in UVMClick.

iii. Are you requesting an Alteration of Informed Consent Procedures? Yes No

This is a request to alter an individual's informed consent or elements of informed consent. Deception in research would be one example when consent would be altered. See [Policies and Procedures Manual](#) for more information about when a subject's consent may be altered. **If yes**, complete the smart form Request for a Waiver of Informed Consent/ Authorization/ Documentation in UVMClick.

iv. Are you requesting a Waiver of Documentation of Informed Consent? Yes No

This request means you are obtaining verbal or implied consent without obtaining the subject's signature on a consent form. See manual for the criteria required to obtain this type of waiver.

If yes, complete the form Request for a Waiver of Informed Consent/Authorization/Documentation in UVMClick.

v. Do you intend to obtain consent from a legally authorized representative? Yes No
If yes, describe the process.

vi. Are you requesting a short form consent process for non-English speaking subjects? Yes No
If yes, please describe. Guidance available in the [Policies and Procedures Manual](#).

b. Consent Process

i. Once a prospective subject is identified, who initiates the informed consent discussion and answers questions presented by the subject or the subject's family?

The PI ([name]) or trained, IRB-approved research staff will initiate the informed consent discussion, answer questions, and explain all study procedures.

ii. Where (in what setting) is the informed consent process initiated? How much time is the subject given to decide?

Informed consent will be initiated in a private office in the UHC building. Participants will be given unlimited time to decide if they wish to participate.

iii. Is the principal investigator present for the initial and subsequent informed consent discussions with the subject?

The PI ([name]) and/or trained, IRB-approved research staff will be present and the PI will be continuously available to answer questions and explain all study procedures at any time.

iv. What other method of documentation is used to record the informed consent process, in addition to the executed consent form? See an [example of documentation](#) of the informed consent **process** under consent templates on our forms page.

N/A

Information Withheld From Subjects: Will any information about the research purpose and design be withheld from potential or participating subjects? If so, explain and justify the non-disclosure and describe plans for post-study debriefing.

Not applicable

Research Data Management Plan: The Research Data Management and Security Plan form must be completed. The form, along with guidance, can be found in our [forms library](#) and must be submitted with your initial application.

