OAT + PET. In addition to receiving standard buprenorphine- or methadone-maintenance treatment as described above and completing monthly assessments, OAT+PET participants will also receive 12 individual sessions of PET. Beginning in Study Week 1, OAT+PET participants will complete weekly 60-minute PET sessions provided by a doctoral- or master's-level therapist trained in PET. Therapy sessions will be conducted at our research clinic in UHC or remotely via UVM's institutionally supported Zoom platform to reduce the risk of COVID-19 transmission. During Sessions 1-2 and prior to beginning the imaginal and in vivo exposures that are the focus of later PET sessions (Foa et al., 2019), participants will receive education about PTSD, the rationale for PET, and breathing retraining techniques as a method for managing PTSD-associated arousal. During Session 3, participants will work with the therapist to provide an initial description of their traumatic event, develop an exposure hierarchy for in vivo exposures, and the first in vivo exposure exercise will be assigned for homework. Weekly in vivo exposure exercises will be assigned at each subsequent session and involve intentional and gradual exposure to real-life trauma reminders that have been previously avoided but are not inherently harmful. Session 4 will be the first session to include imaginal exposure, in which the participant will describe the traumatic event in detail. Each imaginal exposure will be recorded and participants will be instructed to listen to the recording daily as part of their weekly homework assignment. This process is repeated until the final session, which will also include a review of treatment progress. Although PET sessions will be largely informed by conventional prolonged exposure (Foa et al., 2019), we will make the following modifications to support the effective delivery of PET in a clinical population with concurrent PTSD and OUD and facilitate future dissemination efforts: (a) sessions will be approximately 60 minutes in duration, as 60-minute PET sessions promote similar reductions in PTSD symptoms as the more traditional 90-minute sessions (Nacasch et al., 2015); (b) participants will receive psychoeducation regarding the association between PTSD and SUD symptoms; and (3) participants will complete diaphragmatic breathing at the end of each

imaginal exposure exercise in order to reduce distress to baseline levels.

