OAT + Incentivized PET. Participants randomized to the OAT+PET⁺ condition will receive the procedures noted above for the OAT+PET group plus monetary incentives delivered contingent upon completion of PET sessions. The incentive program will follow the general parameters of the program we developed to promote and sustain abstinence from licit and illicit drugs across a variety of clinical populations (Alessi et al., 2004; Dunn et al., 2008, 2010; Heil et al., 2003, 2004; Higgins et al., 1991, 2004; Roll et al., 1996; Roll & Higgins, 2000; Sigmon et al., 2016). Participants will earn vouchers that have monetary value for attending scheduled PET appointments. Vouchers will be given to participants immediately following completion of each session. No cash will be provided to patients; rather, subjects will be able to submit vouchers to a research assistant in exchange for gift cards that they can use for purchase of retail items and services in the local community. The initial session will be worth \$20. Each consecutive attended session will increase the voucher amount by \$5 such that the 2nd consecutive session will be worth \$25, the 3rd \$30 and so on (Table 1).

To support completion of the full 12-week PET protocol, we will incorporate additional strategically-placed bonuses into the reinforcement schedule with the goal of maximizing the percentage of subjects who complete the full 12-session protocol. Bonuses have been a mainstay of our voucher-based interventions with other challenging populations (Alessi et al., 2004; Dunn et al., 2008, 2010; Higgins et al., 1991; Roll et al., 1996, Roll & Higgins, 2000; Sigmon et al., 2016). First, to support consistent (vs. sporadic) attendance, participants will receive a \$50 bonus for every two consecutive sessions attended (Table 1). Second, to support completion of the full PET protocol, participants will receive a \$100 bonus upon completion of Session 12.

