Missed sessions will earn no vouchers and will reset the voucher values for the next attended session back to the initial \$20 value. Two consecutive attended PET sessions following a reset will return the voucher value back to the value immediately prior to the missed appointment. In prior studies, we demonstrated that this reset mechanism helps to maintain the momentum of behavioral change (Roll et al., 1996; Roll & Higgins, 2000). Overall, participants who are randomized to the OAT+PET⁺ group and who attend every PE session as scheduled can earn a maximum of \$920 combined across both regular and bonus incentive schedules.

Table 1 – OAT+PET+ incentive program

Session	Incentive	Bonus
1	\$20	
2	\$25	\$50
3	\$30	
4	\$35	\$50
5	\$40	
6	\$45	\$50
7	\$50	
8	\$55	\$50
9	\$60	
10	\$65	\$50
11	\$70	
12	\$75	\$100
Total earnings	\$570	\$350

Describe required screening procedures performed before enrollment and while on study.

When interested individuals contact the RA, s/he will use a brief phone screen to make a preliminary determination about the potential participant's eligibility. Those who are interested in participating and appear to be eligible will be scheduled for a longer intake screening assessment.

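### Does the incentive schedule contradict itself on whether a participant who attends every session can earn $920 or $970?

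*Combined protocol and SAP*

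**What the plan says.** The incentive programme is described under Experimental conditions, OAT + Incentivized PET, and again under Financial Considerations, Compensation for participation.

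- **Vouchers.** "The initial session will be worth \$20", and "Each consecutive attended session will increase the voucher amount by \$5". The PET course is 12 sessions long ("OAT+PET participants will also receive 12 individual sessions of PET"), and OAT+PET+ follows the same course.
- **Consecutive-attendance bonus.** Introduced as the first bonus: $50, described as a "bonus for every two consecutive sessions attended (Table 1").
- **Completion bonus.** Introduced as the second bonus: "participants will receive a \$100 bonus upon completion of Session 12".
- **Table 1.** It lists all 12 sessions. The bonus column shows $50 at Sessions 2, 4, 6, 8 and 10 and $100 at Session 12. The column totals are $570 for vouchers and $350 for bonuses.
- **Maximum.** The methods text puts it at $920, "combined across both regular and bonus incentive schedules". The compensation section repeats $920, "for session participation combined across both regular and bonus incentive schedules".

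**The concern.** The two bonuses are introduced as separate items with separate purposes: one rewards steady attendance, the other completion. The first is promised for each pair of sessions and carries no exception. A reader of the prose alone would add them, and Sessions 11 and 12 would then earn both the $50 and the $100. Table 1 shows only the $100 there.

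If this were a real conflict, it would sit in an awkward place. The incentives are the only planned difference between OAT+PET+ and OAT+PET. The disputed payment falls on the final session, and the bonuses exist to get participants to that session. The maximum payment reported to the IRB would also be too low by $50.

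**Working it through.** **Inputs** (OAT + Incentivized PET, and Table 1): starting voucher $20; step $5; 12 sessions; pair bonus $50; completion bonus $100.

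**1. Reproduce the plan's figure.**

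- Vouchers: session k pays 20 + 5(k - 1), so Session 12 pays $75. The sum is 12 x (20 + 75) / 2 = $570, which matches Table 1.
- Bonuses as tabulated: 5 x $50 + $100 = $350, which matches Table 1.
- Total: $570 + $350 = $920, which matches both stated maxima.

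**2. Read the prose without the table.**

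| Reading | Bonuses | Total |
|---|---|---|
| Table 1: the $100 stands alone at Session 12 | 5 x $50 + $100 = $350 | $920 |
| Separate pairs, both bonuses paid at Session 12 | 6 x $50 + $100 = $400 | $970 |
| Overlapping pairs (1-2, 2-3, ..., 11-12), both paid at Session 12 | 11 x $50 + $100 = $650 | $1,220 |

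The prose alone does not single out $970, because it leaves open whether pairs may overlap. Table 1 settles that: pairs do not overlap and they end on even-numbered sessions. To reach $970 one must rely on the table to count the pairs and then disregard its Session 12 row.

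**3. Size of the gap.**

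- Per full attender: $970 - $920 = $50. That is 50/920 = 5.4% of the maximum and 50/350 = 14% of the bonus total.
- At Session 12 itself: $75 + $100 = $175 as tabulated, against $75 + $50 + $100 = $225 if both bonuses are paid.
- For the arm: at most 45 x $50 = $2,250, and only if all 45 OAT+PET+ participants in the main trial attended every session.

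**4. Does it reach the analysis?** Statistical Considerations uses CAPS-5 at Weeks 4, 8 and 12, a mixed model on treatment condition and timepoint, and a sample size based on an 8-point difference in mean CAPS-5 change. No payment amount enters any of these. Vouchers are handed over after each session, so the disputed $50 would arrive only once the twelfth session was finished. It could affect attendance only through what a participant had been told to expect for the last sessions.

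**The case for a change.** The best counter-argument is that Table 1 covers only perfect attendance. After a missed session the vouchers reset, and staff must then work from the prose, so the prose is not mere commentary on the table.

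Take a participant who misses only Session 5. Assume that sessions keep their scheduled numbers and that pair counting restarts after the miss. The pairs are 1-2, 3-4, 6-7, 8-9 and 10-11, which with the completion bonus gives 5 x $50 + $100 = $350. That equals the tabulated bonus total for someone who missed nothing, which is an odd result for a scheme meant to reward unbroken attendance.

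This much stands: the text does not say how pairs are counted after a miss, and it does not say how the two bonuses combine at Session 12. It does not establish two rival definitions of the programme. For full attendance, which is the case the $920 describes, the bonus sentence sends the reader to a complete schedule that gives one answer.

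The missed-session case also limits how far the concern reaches. On the same counting assumption, a participant who misses only Session 3 has pairs 1-2, 4-5, 6-7, 8-9 and 10-11. Session 12 is then unpaired and no extra $50 arises, although Sessions 11 and 12 were both attended. The gap therefore cannot be said to touch everyone who attends the last two sessions.

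Finally, Study Design provides for 30 pilot participants, 10 per condition, and names the incentive schedule among the logistical matters the pilot is meant to settle. A question of who is paid what at Session 12 is the kind of point such a pilot brings up.

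**Conclusion.** No change to the plan is needed. The arithmetic behind the concern is right: adding the bonuses without the table gives $970, against a stated $920. The conclusion drawn from it is too strong. Table 1, its column totals and both stated maxima agree on $920, and the bonus sentence cites that table. The maximum reported to the IRB is therefore correct under the schedule the plan sets out. Whether the consent form carries the same figure cannot be judged, since the consent pages are not part of the text available.

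The residue is clerical: a missing clause on how the two bonuses combine at Session 12, worth at most $50 per participant who attends all 12 sessions. A team paying from Table 1 would run a coherent incentive arm. The comparison of OAT+PET+ with OAT+PET, the power statement and the trial's conclusions would be the same with or without the clause. This rests on two assumptions: that staff pay full attenders from the cited table, and that $50 at the last session does not materially alter attendance in a programme already offering $175 for that session.
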